8.3.8 Hy's Law

Cases where a participant shows elevations in liver biochemistry may require further evaluation and occurrences of AST or ALT $\geq 3 \times$ ULN together with total bilirubin $\geq 2 \times$ ULN may need to be reported as SAEs. Please refer to [Appendix E](#) for further instruction on cases of increases in liver biochemistry and evaluation of HL.

8.3.9 Reporting of Serious Adverse Events

All SAEs have to be reported, whether or not considered causally related to the study intervention, or to the study procedure(s). All SAEs will be recorded in the eCRF.

If any SAE occurs in the course of the study, then investigators or other site personnel inform the appropriate AstraZeneca representatives within one day ie, immediately but **no later than 24 hours** of when he or she becomes aware of it.

The designated AstraZeneca representative works with the investigator to ensure that all the necessary information is provided to the AstraZeneca Patient Safety data entry site **within 1 calendar day** of initial receipt for fatal and life-threatening events **and within 5 calendar days** of initial receipt for all other SAEs.

For fatal or life-threatening AEs where important or relevant information is missing, active follow-up is undertaken immediately. Investigators or other site personnel inform AstraZeneca representatives of any follow-up information on a previously reported SAE within one calendar day ie, immediately but **no later than 24 hours** of when he or she becomes aware of it.

For further guidance on the definition of an SAE, see [Appendix B](#).

The reference document for definition of expectedness/listedness for MEDI3506 is the IB.

8.3.10 Pregnancy

All pregnancies and outcomes of pregnancy should be reported to AstraZeneca except if the pregnancy is discovered before the study participant has received any study intervention.

8.3.10.1 Maternal Exposure

If a participant becomes pregnant during the course of the study, study intervention should be discontinued immediately.

Pregnancy itself is not regarded as an AE unless there is a suspicion that the study intervention may have interfered with the effectiveness of a contraceptive medication. Congenital abnormalities/birth defects and spontaneous miscarriages should be reported and handled as SAEs. Elective abortions without complications should not be handled as AEs. The outcome of all pregnancies (spontaneous miscarriage, elective termination, ectopic pregnancy, normal birth or congenital anomaly) should be followed up and documented even if the participant was discontinued from the study.

If any pregnancy occurs in the course of the study, then the investigator or other site personnel informs the appropriate AstraZeneca representatives within one day ie, immediately but **no later than 24 hours** of when he or she becomes aware of it.

The designated AstraZeneca representative works with the investigator to ensure that all relevant information is provided to the AstraZeneca Patient Safety data entry site within one or 5 calendar days for SAEs (see Section 8.3.9) and within 30 days for all other pregnancies.

The same timelines apply when outcome information is available.

The PREGREP module in the eCRF is used to report the pregnancy.

8.3.10.2 Paternal Exposure

Male participants should refrain from fathering a child or donating sperm during the study and for 12 weeks following the last dose of study intervention.

Pregnancy of the participant's partners is not considered to be an AE. However, the outcome of all pregnancies (spontaneous miscarriage, elective termination, ectopic pregnancy, normal birth or congenital anomaly), occurring from the date of the first dose until the end of the follow-up period (SV11 [Week 16]) or date of last contact should, if possible, be followed up and documented in the Pregnancy Report Form. Consent from the partner must be obtained before the Pregnancy Report Form is completed.

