4 STUDY DESIGN

4.1 Overall Design

Study D9181C00001 is a Phase II, randomised, double-blind, placebo-controlled, parallel-group, proof-of-concept study to evaluate the efficacy, safety, PK and immunogenicity of MEDI3506 in adult participants with uncontrolled moderate-to-severe asthma on SOC.

Approximately 228 participants will be randomised in a 1:1:1 ratio to achieve 216 evaluable participants. Participants will receive CCI mg MEDI3506, CCI mg MEDI3506, or placebo CCI by SC injection for a total of C doses. The randomisation will be stratified according to cough sub-study participation. Note that the exploratory cough sub-study may not be activated in all countries.

Participants who fail screening can be re-screened.

Participants will be enrolled in this study for up to 29 weeks. The study comprises of 3 periods including the screening period of up to 5 weeks, an intervention period of 16 weeks, and a follow-up period of 8 weeks.

Safety data from this study will be provided to the MEDI3506 DSMB (see Appendix A 4).

Screening Period

- Participants will sign ICF and be assessed for study eligibility at SV1 (Sections 5.1 and 5.2).
- Participants assessed to have uncontrolled asthma at SV1 will undergo further baseline assessments at SV1 (see Table 1). Participants will then record adherence to their SOC asthma controller and reliever medication for a minimum period of 14 days before returning for SV2.
- At SV2, participants whose asthma remains uncontrolled despite acceptable adherence to asthma controller medication ($\geq 70\%$ adherence [days] to controller medication documented in eDiary and $ACQ-6 \geq 1.5$) will undergo further screening assessments (including echocardiogram). Participants who continue to meet all eligibility criteria will be asked to attend SV4 (randomisation) 6 to 14 days following SV2.
 - A subset of participants (up to $n = 60$, see Section 9.2 for details) who have provided optional informed consent to participate in the sub-study, will also undergo 24-hour objective cough monitoring at home, as part of an exploratory cough sub-study, commencing at SV2 and again at SV10.

Intervention Period

- Participants will be randomised at SV4 (Day 1).
- Study interventions will be administered CCI at CCI, as well as the final dose administered at CCI.
- The primary endpoint will occur at SV10 (Week 16 post initial dose of study intervention).

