- During the intervention period, participants will be required to take their asthma controller therapy regularly, complete the eDiary and perform lung function tests using a spirometry device at home regularly.
- An automated alert to the participant and site will be triggered if there is a clinically significant deterioration in any of the eDiary data points (as defined in Section 8.1.5) for > 2 days, prompting the participant to contact the investigator for further assessment of a possible asthma exacerbation. Alerts will only be received by site when eDiary uploads/syncs on adequate mobile or broadband signal; therefore, participants may initiate contact with the investigator for assessment of possible exacerbation regardless of any prompts from the site, or the eDiary and spirometry.

Follow-up Period

- Participants who complete the 16-week intervention period visit will complete an 8-week post-treatment follow-up period.
- Participants will be required to take their SOC asthma controller medications throughout the follow-up period.

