- 9 Participants must demonstrate ability to perform acceptable inhaler and spirometry techniques.
- 10 Able and willing to comply with the requirements of the protocol including ability to read, write, be fluent in the translated language of all participants facing questionnaires used at site, and use electronic devices eg, eDiary and spirometry.

Weight

- 11 Bodyweight ≥ 40 kg and BMI < 40 kg/m².

Reproduction

- 12 For female participants of childbearing potential (see [Appendix I](#) for definition of childbearing potential):
 - A negative serum pregnancy test at SV1.
 - A negative urine pregnancy test at SV2 and prior to administration of study intervention at SV4 (randomisation).
- 13 Female participants of childbearing potential who are sexually active with a male partner must agree to use a highly effective method of contraception from screening until the end of the follow-up period at SV12 (Week 24) of the study. See [Appendix I](#) for definitions of childbearing potential and highly effective methods of contraception.
 - In countries where spermicide is available, it is strongly recommended for the male partner of a female participant of childbearing potential to also use male condom plus spermicide throughout this period.
 - In countries where spermicide is not available, it is strongly recommended for the male partner of a female participant of childbearing potential to also use male condom throughout this period.
- 14 There are no contraception requirements for female participants who are not of childbearing potential. However, all female participants should refrain from egg cell donation and breastfeeding throughout the study.

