- 15 In countries where spermicide is available, male participants who are sexually active with a female partner of childbearing potential must agree to use a male condom with spermicide and another highly effective method of contraception during the intervention and follow-up periods from SV4 (Day 1) through to SV12 (Week 24) of the study. In countries where spermicide is not available, male participants who are sexually active with a female partner of childbearing potential must agree to use a male condom and another highly effective method of contraception during the intervention and follow-up periods from SV4 (Day 1) through to SV12 (Week 24) of the study. See [Appendix I](#) for definitions of childbearing potential and highly effective methods of contraception. Male participants should also refrain from biologically fathering a child or donating sperm during the same period.

Informed Consent

- 16 Provision of signed and dated, written informed consent (and any locally required authorisation eg, data privacy) for study participation which includes mandatory

genotyping (study objective). Note: If a participant declines to participate in the mandatory genotyping component of the study, the participant will not be included in the study.

- 17 **Optional:** provision of signed and dated written Optional Genetic Research Information informed consent prior to collection of samples for optional genetic research that supports Genomic Initiative.

Type of Participant and Disease Characteristics

- 18 Participants with documented evidence of asthma as demonstrated by either:
- Post-BD reversibility of $FEV_1 \geq 12\%$ and ≥ 200 mL (15 to 60 min after administration of 4 puffs of albuterol/salbutamol), within 12 months prior to SV1, or at SV1 or SV2. Note: if the participant cannot perform post-BD spirometry at SV1 or needs to perform a repeat assessment of post-BD spirometry, it is also acceptable to assess this criterion at SV2, **or**
 - Positive methacholine challenge test within the 12 months prior to SV1. A positive result is defined as a $PC_{20} \leq 8$ mg/mL.
- 19 Documented history of ≥ 1 asthma exacerbation in 24 months prior to SV1 (see Section 8.1.5 for definitions of acceptable documentation and asthma exacerbation).
- 20 Morning pre-BD $FEV_1 \geq 40\%$ predicted normal and > 1 L at SV1.

Criteria to be Assessed for Exploratory Cough Sub-study

Informed Consent

- 21 Provision of written dated separate ICF for the exploratory cough sub-study.

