9.5 Interim Analyses

No formal interim analyses are planned for this study.

The primary analysis will occur once all participants have either completed the SV10 (Week 16) assessments or have withdrawn from the study. The sponsor staff will be fully unblinded following the Primary Analysis Clinical Data Lock. Investigators, participants and site staff will not be made aware of unblinded treatment assignments for individual participants who are in the follow-up period until these participants have completed the study. The final analysis will occur when all participants have completed the follow-up period at SV12 (Week 24) or have withdrawn from the study.

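### Section 8.3.10.2 labels the end of follow-up SV11 [Week 16], a visit and week that do not go together; follow-up ends at SV12 (Week 24)

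*Protocol*

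**What the plan says.** Section 8.3.10.2 (Paternal Exposure) defines which partner pregnancies are to have their outcomes followed up and documented: those occurring from the date of first dose "until the end of the follow-up period (SV11 [Week 16]) or date of last contact".

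Elsewhere the protocol describes a different timetable:

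- Section 4.1 sets "an intervention period of 16 weeks, and a follow-up period of 8 weeks".
- Inclusion Criterion 13 runs contraception for women "from screening until the end of the follow-up period at SV12 (Week 24) of the study".
- Inclusion Criterion 15 runs contraception for men "during the intervention and follow-up periods from SV4 (Day 1) through to SV12 (Week 24) of the study", and adds: "Male participants should also refrain from biologically fathering a child or donating sperm during the same period".
- Section 9.5 times the final analysis to the completion of follow-up at SV12 (Week 24). SAP Sections 4 and 5 repeat this.

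**The concern.** The bracket is the only place in the partner-pregnancy rule that names a visit, and its two halves disagree with each other and with the words they are meant to explain. Week 16 is the primary-endpoint visit, where follow-up begins. SV11 is the middle follow-up visit.

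The window decides which partner pregnancies are covered. It does not cut short the outcome follow-up of a pregnancy already inside it. A site that takes its cut-off from the bracket could leave out a partner pregnancy arising late in follow-up.

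Such a case would be informative. Table 3 of the protocol lists reproductive toxicity as a potential risk because embryo-foetal development studies have not been done. Pregnancy outcomes are therefore information the sponsor does not yet have.

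**Working it through.** This is schedule arithmetic and cross-reference; no sample-size formula applies.

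**Inputs** (nominal days from protocol Table 2; the Week 16, 20 and 24 rows are the same in SAP Table 3, Section 3.1.4)

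| Visit | Week | Study day | Period |
|---|---|---|---|
| SV4 | 0 | 1 | Randomisation, first dose |
| SV10 | 16 | 113 | End of intervention |
| SV11 | 20 | 141 | Follow-up |
| SV12 | 24 | 169 | Follow-up, last visit |

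**Step 1: does the label match a row?** Study day = 7 × week + 1. Week 16 gives 7 × 16 + 1 = 113, which is SV10. SV11 is Day 141, and (141 − 1)/7 = Week 20. No row pairs SV11 with Week 16.

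**Step 2: when does follow-up end?** From Section 4.1, 16 + 8 = Week 24. Day = 7 × 24 + 1 = 169, which is SV12. This agrees with Inclusion Criteria 13 and 15, Section 9.5, and SAP Sections 4 and 5.

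**Step 3: what does each reading leave out?** The intended window is 169 − 1 = 168 days, of which follow-up is 169 − 113 = 56 days.

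| Reading of the bracket | Window ends | Days left out | Share of window | Share of follow-up |
|---|---|---|---|---|
| Week 16 | Day 113 | 169 − 113 = 56 | 56/168 = 1/3 | 56/56 = all |
| SV11 | Day 141 | 169 − 141 = 28 | 28/168 = 1/6 | 28/56 = half |
| SV12 (Week 24) | Day 169 | 0 | 0 | 0 |

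**Step 4: does the rest of Section 8.3.10.2 fit?** Its first sentence asks men not to father a child or donate sperm during the study and for 12 weeks after the last dose. The dosing schedule is redacted, so the date of the last dose is an assumption. SAP Section 3.5.2 describes vital signs around dosing, with SV9 (Week 12) the latest such visit. If SV9 is the last dosing visit, the restriction ends at Week 12 + 12 = Week 24, the same as SV12.

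On the same assumption, Week 16 is 4 weeks after the last dose. Section 5.3 equates 16 weeks with 5 half-lives, so one half-life is 16/5 = 3.2 weeks. The Week 16 reading would then close the window 4/3.2 = 1.25 half-lives after the last dose, and the SV11 reading 8/3.2 = 2.5 half-lives after it.

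**The case against.** The strongest reply is that the governing words are already right. The sentence says that the window runs to the end of follow-up or to last contact, and the bracket only illustrates it. Because the bracket contradicts itself, a careful site would check the schedule and find SV12. Section 8.3.10, which heads both pregnancy subsections, separately asks for all pregnancies and outcomes to be reported, except pregnancies discovered before any dosing.

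The clause is also a best-effort instruction. Partner pregnancy is not classed as an adverse event, documentation is asked for where possible, and the partner must consent. A case could go undocumented even with the correct label. The SAP's output list (Appendix C) shows no pregnancy table or listing, so no planned output would change.

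The 28 and 56 days are differences between nominal visit days under literal readings. They are not an expected loss of cases: the documents give no expected number of partner pregnancies.

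All of this stands, and it is why the point ranks low. It does not make the bracket correct. Section 8.3.10.2 is the specific rule for partner outcomes, and a site looking for a cut-off visit will look at the bracket. The last-contact alternative does not say whether the earlier or the later date applies, so it does not reliably repair the error.

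**Conclusion.** The concern holds. The label is wrong as written: the pair does not exist in the schedule, and neither half of it marks the end of follow-up. The text is current and unredacted. Taken literally, it shortens the partner-pregnancy window by 28 nominal days (SV11) or 56 nominal days (Week 16) out of 168, before allowing for the ±3-day visit windows. The practical risk is small, and this is a point to consider, not a defect in the design. Efficacy analyses, power and type I error are untouched.

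The conclusion rests only on the visit schedule and the stated period lengths. The half-life comparison is supporting and depends on SV9 being the last dosing visit.

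**What to change.** In Section 8.3.10.2, replace (SV11 [Week 16]) with (SV12 [Week 24]), in the next protocol amendment or in a clarification letter to sites. The cost is one bracket of wording, with no added visits, procedures or participants.

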8.3.11 Medication Error

If a medication error occurs in the course of the study, then the investigator or other site personnel informs the appropriate AstraZeneca representatives within one day ie, immediately but no later than 24 hours of when he or she becomes aware of it.

The designated AstraZeneca representative works with the investigator to ensure that all relevant information is completed within one (Initial Fatal/Life-Threatening or follow-up

Fatal/Life-Threatening) or 5 (other serious initial and follow-up) calendar days if there is an SAE associated with the medication error and within 30 days for all other medication errors.

The definition of a medication error can be found in [Appendix B](#).

8.4 Overdose

An overdose is defined as a participant receiving a dose of study intervention in excess of that specified in the IB, unless otherwise specified in this protocol.

- An overdose with associated AEs is recorded as the AE diagnosis/symptoms on the relevant AE modules in the eCRF and on the Overdose eCRF module.
- An overdose without associated symptoms is only reported on the Overdose eCRF module.

If an overdose on an AstraZeneca study drug occurs in the course of the study, the investigator or other site personnel will inform appropriate AstraZeneca representatives immediately, but **no later than 24 hours** of when he or she becomes aware of it.

The designated AstraZeneca representative works with the investigator to ensure that all relevant information is provided to the AstraZeneca Patient Safety data entry site within 1 or 5 calendar days for overdoses associated with an SAE (see Section 8.3.9) and within 30 days for all other overdoses.

The designated sponsor representative works with the investigator to ensure that all relevant information is provided to the sponsor's Patient Safety data entry site.

8.5 Human Biological Sample Biomarkers

8.5.1 Human Biological Samples

Instructions for the collection and handling of biological samples will be provided in the study specific laboratory manual. Samples should be stored in a secure storage space with adequate measures to protect confidentiality. For further details on handling of human biological samples see [Appendix C](#).

- Samples will be stored for a maximum of 15 years after the end of the study in line with consent and local requirements, after which they will be destroyed/repatriated.

- PK samples will be disposed of after the Bioanalytical Report finalization or six months after issuance of the draft Bioanalytical Report (whichever is earlier), unless consented for future analyses.
 - PK samples may be disposed of or anonymised by pooling. Additional analyses may be conducted on the anonymised, pooled PK samples to further evaluate and validate the analytical method. Any results from such analyses may be reported separately from the CSR.
- Remaining ADA sample aliquots will be retained at AstraZeneca or its designee for a maximum of 15 years after the end of the study. Additional use includes but is not limited to further characterisation of any ADAs, confirmation and/or requalification of the assay as well as additional assay development work. The results from future analysis will not be reported in the CSR.

8.5.2 Pharmacokinetics

- Serum samples will be collected for measurement of serum concentrations of MEDI3506 as specified in the SOA (Table 1 and Table 2).
- Samples may be collected at additional time points during the study if warranted and agreed upon between the investigator and the sponsor eg, for safety reasons. The timing of sampling may be altered during the course of the study based on newly available data (eg, to obtain data closer to the time of peak or trough matrix concentrations) to ensure appropriate monitoring.
- Samples will be collected, labelled, stored, and shipped as detailed in the laboratory manual.
- Samples from participants who receive placebo may be analysed at minimum selected time points to confirm no dosing with MEDI3506 took place.

8.5.2.1 Determination of Drug Concentration

The nominal timing of vital signs, ECGs, and blood draws is described in the SOA (Table 1 and Table 2). The time of the first SC injection will be recorded for each participant as the timings will be required for analysing the PK data.

Serum will be collected to evaluate the PK of MEDI3506 according to the SOA. MEDI3506 concentration in serum will be measured utilizing a validated assay method.

Instructions for sample collection, processing, storage, and shipment can be found in a separate laboratory manual provided to sites.

8.5.3 Immunogenicity Assessments

Blood samples for determination of ADA in serum will be assayed by bioanalytical test sites operated by or on behalf of AstraZeneca, using an appropriately validated bioanalytical

method. Tiered analyses will be performed to include screening, confirmatory, and titre assay components. Full details of the methods used will be described in a separate report.

ADA samples may also be further tested for characterisation of the ADA response, including possible assessment of neutralising antibody.

Samples will be collected, labelled, stored, and shipped as detailed in the laboratory manual.

8.5.4 Pharmacodynamics

There are no established PD measures for MEDI3506. For exploratory biomarkers that may indicate a PD effect, see Section [8.5.5](#).

